##### **Serious Adverse Events (SAE)**

In accordance with NHLBI and the OHRP Management Charter, a serious adverse event (SAE) is defined as meeting one of the following criteria:

- 1) resulting in fatality or posing a life-threatening risk;
- 2) causing severe and permanent disability;
- 3) requiring hospitalization or prolonged hospitalization;

- 4) leading to congenital abnormalities/birth defects in offspring;
- 5) being determined by investigator as a medical event that causes significant harm to the patient, necessitating medication or surgical intervention to prevent other conditions as outlined in the SAE (e.g., death, permanent disability, hospitalization).

#### ***4.8 Missing data***

Missing data will be assumed missing completely at random. In general, no imputation will be applied unless otherwise specified. For subjects lost to follow-up or withdraw from the study, all available data prior to their loss of follow-up were included in the analysis.

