### 2.1 Study design

This study was a multicentre, double-blind, parallel randomized controlled study using a 1:1 parallel control design. A total of 200 patients with coronary heart disease combined with cognitive decline but no dementia will be enrolled from 8 centres (Beijing Anzhen Hospital affiliated to Capital Medical University, Peking University Third Hospital, The second hospital of Chifeng, The First Affiliated Hospital of Hebei North University, Handan Central Hospital, The First Hospital of Hebei Medical University, Beijing Sixth Hospital, Inner Mongolia Ordos Central Hospital Kangbashi Department). All patients were stratified and randomly assigned to the cognitive digital therapy group and the positive control group according to age and educational level, and were given cognitive training at least 5 times a

week for at least 30 minutes each time for a total of 12 weeks. All subjects were interviewed at 12 weeks. After completing the 12-week visit, the researchers will unblind the subjects, the positive control group will end the intervention, and the cognitive digital therapy group will repeat the intervention 1:1 randomization: One group ended the cognitive training, and the other group continued the training until 24 weeks. Each patient will be followed up to 24 weeks. The primary outcome was the proportion of improvement in overall cognitive function at 12 weeks, defined as 0.67 standard deviation (SD) above baseline cognitive function as measured by the Basic Cognitive Ability Test (BCAT). (see Fig. 1)

Fig. 1 Participant flow through study

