### **4. Statistic**

#### *4.1 General analysis considerations*

The analyses will be conducted using SAS 9.4 statistical software. Descriptive statistics will be computed, including the sample size (n), means, standard deviations, medians, and inter and frequency counts and percentages for categorical variables. The efficacy endpoint will be summarized by assessment time points (baseline, 12, 24 weeks) and by intervention groups. Data will be examined for skewness and outliers. Categorical variables are shown as n (%), and continuous variables as mean (standard deviation [SD]) if normally distributed or median (interquartile range [IQR]) if there was a skew distribution. Shapiro-Wilktest will be used to test the normality, the data will be presented as a median (interquartile range) and transformed to approximate a normal distribution. If transformation is not feasible, a

Wilcoxon test can be performed.

The following descriptive data will be present by intervention groups:

Demography characteristics:

Gender(female%), Age(n), Education level (middle school or below, high school or above)

Laboratory measure(n):

BMI, Pulse, Blood pressure (baseline,12 weeks and 24 weeks), Blood test (FBG, TG, etc.),

Electrocardiogram result (sinus rhythm/other), Doppler echocardiography (LVEF, etc.)

Medical/Cardiovascular disease history

Drug usage: Types of drugs and dosages

Self-reported disease/surgical history: Hypertension, Coronary artery disease, Coronary artery bypass/Stenting surgery, neurological disease etc.

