#### *4.4.2 Main secondary efficacy analyses*

The main secondary efficacy analyses will include comparison the intervention group and the control group for the 12-week endpoint analysis and three study groups after the re-randomization at 12 weeks, including the continue training group, stop training group and the control group at the baseline randomization, for the 24 weeks endpoint analysis. All statistical tests of the secondary analyses will be 2-sided, both 95% confidence intervals and p values will be reported.

- 1) The mean value of changes in scores of global cognitive functions from baseline to 12 weeks will be compared using independent t-test between the intervention group and control group. In cases any of domains' score not following normal distribution, if the transformation is not feasible, either the Wilcoxon test or Friedman M test will be used.
- 2) Difference in the proportion of improvement in global cognitive function after 24 weeks will be compared using Pearson chi-square test between continue training group and control group. Adjustment will be performed if necessary.

- 3) The mean value of changes in scores of global cognitive functions from baseline to 24 weeks will be compared using independent t-test between continue training group and control group. Adjustment will be performed if necessary.
  
- 4) The mean value of changes in scores of global cognitive functions from baseline to 24 weeks will be compared using independent t-test between the stop training group and control group. Adjustment will be performed if necessary.

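### The week-24 mean-change comparisons are separate t-tests that use no week-12 scores, forgoing roughly 3% to 26% of their variance depending on an unstated correlation and later loss; a minor loss of precision on secondary endpoints

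*SAP*

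**What the plan says.** Section 2.1 describes a 1:1 randomisation to training or positive control for 12 weeks. After the week-12 visit, patients are unblinded and control training ends; then "the cognitive digital therapy group will repeat the intervention 1:1 randomization", one half stopping and the other continuing to week 24.

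Section 4.4.2 sets up three groups for week 24, "including the continue training group, stop training group and the control group at the baseline randomization". Item 3 says that mean changes from baseline to 24 "weeks will be compared using independent t-test between continue training group and control group". Item 4 does the same for the other half: changes to 24 "weeks will be compared using independent t-test between the stop training group and control group". Both items end "Adjustment will be performed if necessary", with no covariate, model or trigger named.

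Section 4.1 has the efficacy endpoint "summarized by assessment time points (baseline, 12, 24 weeks) and by intervention groups", so week-12 scores are collected in every group. Section 4.8 assumes data are missing completely at random, plans no imputation in general, and says that for patients lost or withdrawn "all available data prior to their loss of follow-up were included in the analysis".

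**The concern.** A t-test on change to week 24 needs a week-24 score. A patient measured at baseline and week 12 but lost afterwards has none and cannot enter item 3 or item 4. For these endpoints the 4.8 sentence therefore has no method behind it.

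The tests also leave out something the design provides. Continue and stop were one randomised arm on the same training until they were split after week 12, so they share one week-12 population mean. The stop group's week-12 scores therefore carry information on the continue group's course, and the reverse. Each t-test discards this and compares about a quarter of the trial with about a half.

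What is at stake is precision on whether the effect lasts, which section 2 gives as a purpose of the follow-up to week 24.

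**Working it through.** **The plan's own figure.** Section 2.3 sizes only the primary endpoint: 30% v 10%, two-sided 0.05, 90% power. The unpooled formula gives (1.960 + 1.282)² × (0.30×0.70 + 0.10×0.90) / 0.20² = 10.51 × 0.30 / 0.04 = 78.8, so 79 per arm. Then 79 / 0.8 = 98.75, so 99 per arm and 198 in all. This reproduces. The SAP gives no SD, correlation or power for the week-24 mean changes, so the rest is relative to the t-test variance.

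**Inputs.**
- Allocation continue : stop : control = 1 : 1 : 2, from the two 1:1 randomisations in 2.1. As an illustration, 200 planned less 20% gives 160, or 40, 40 and 80. The percentages depend on the ratio and the loss rates, not on the total, so enrolling 224 does not change them.
- r, the correlation between the 12-week and 24-week changes: assumed, 0.3 to 0.8.
- Loss after week 12: assumed. Section 2.3 gives only a 3-month rate.
- Equal variance s² in all groups, with the covariance treated as known.

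**No loss after week 12.** The variance of continue minus control is:
- t-test: s²(1/40 + 1/80) = 3s²/80
- joint model, common week-12 mean for continue and stop: s²[(1 − r²)/40 + r²/80 + 1/80]

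The saving is s²(r²/40 − r²/80) = s²r²/80. Divided by 3s²/80, this is **r²/3**. Stop minus control gives the same.

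**10% lost by week 12, a further 10% of those randomised lost by week 24.** From 50, 50 and 100 randomised, 45, 45 and 90 are seen at week 12, and 40, 40 and 80 at week 24. The joint variance is s²[(1 − r²)/40 + r²/90 + (1 − r²)/80 + r²/90]. The saving is r²(0.0375 − 0.0222)/0.0375 = **0.407r²**.

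**Ordinary three-arm repeated-measures model** (separate week-12 means for continue and stop). With no later loss the saving is 0. With the loss above, 1/90 becomes 1/45 for the continue group, and the saving is r²(0.0375 − 0.0333)/0.0375 = **0.111r²**.

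| r | common mean, no later loss | common mean, 10% + 10% loss | separate means, 10% + 10% loss |
|---|---|---|---|
| 0.3 | 3.0% | 3.7% | 1.0% |
| 0.5 | 8.3% | 10.2% | 2.8% |
| 0.7 | 16.3% | 20.0% | 5.4% |
| 0.8 | 21.3% | 26.1% | 7.1% |

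At r of 0.5 to 0.7 the routine model thus gains about 0% to 5%. Most of the benefit comes from the common week-12 mean, not from recovering later dropouts.

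**In terms of power.** A variance cut of 8% to 20% shortens the standard error by 4% to 11%. A comparison with 80% power by t-test would have about 83% to 88%.

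**Bias, for illustration only.** Suppose controls with a below-average 12-week change are lost at 30% and everyone else at 5%. For a normal change, each half of the controls lies on average 0.798 SD from the mean. Among retained controls the week-12 mean rises by 0.798 × (0.95 − 0.70)/(0.95 + 0.70) = 0.121 SD. The week-24 mean rises by r times that: 0.060 SD at r = 0.5 and 0.085 SD at r = 0.7. The t-test difference shrinks by that amount. The joint model, conditioning on week 12, removes the shift. If the same selective loss occurs in every group, the shifts cancel.

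**The case against.** A t-test on change is a valid, simple analysis of a secondary endpoint, and nothing here shows that a conclusion would change. The correlation and the later loss rate are assumed, and at r = 0.3 the gain is only 3% to 4%. This stands, and it is why the point is minor.

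The 4.8 sentence can be read generally. A patient lost after week 12 does enter the week-12 primary test and item 1 of 4.4.2, so data before loss are used somewhere. This also stands in part: a reader might infer that 4.8 and 4.4.2 flatly contradict each other, but 4.8 does not promise that every patient enters every test. It is loosely worded, and for the week-24 mean changes no stated method fulfils it.

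The adjustment clause might be said to leave room for a better model. It names nothing, so it cannot count as a plan to use the week-12 scores.

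A reader might also infer that the week-24 t-tests are biased. The SAP does not support that. Under its own missing-data assumption they are unbiased. Bias needs loss after week 12 that depends on the week-12 result differently by group. Unblinding and the end of control training at that visit make this conceivable, but the document reports no such loss, and the scenario above was constructed.

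**Conclusion.** The point holds as a loss of precision. Items 3 and 4 of 4.4.2 use no week-12 scores, so they forgo all of the variance reduction that those scores offer. That reduction is r²/3 of the t-test variance with no later loss (3% to 21% for r from 0.3 to 0.8), and about 4% to 26% with the assumed 10% + 10% loss. It rests on the 1:1:2 allocation, equal variances and an assumed r. Any gain from baseline covariates is separate and not counted.

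It would be wrong to read this mainly as a problem of wasted dropouts, since most of the gain needs the common week-12 mean. It would also be wrong to extend it to the primary endpoint or its sample size, neither of which is affected. Severity: minor.

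**What to change.** In 4.4.2, make the main analysis of items 3 and 4 one repeated-measures model of global BCAT change at weeks 12 and 24:
- unstructured covariance, allowed to differ by group if needed once training diverges;
- a two-arm effect at week 12 (training v control);
- a three-group effect at week 24 (continue, stop, control);
- continue minus control and stop minus control at week 24 reported as contrasts with 95% confidence intervals.

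Keep the t-tests, or the Wilcoxon fallback, as supportive. State what the adjustment clause means or delete it. In 4.8, say that data before loss enter the week-24 mean-change analysis through this model under missing at random. Fix the wording before week-24 outcomes are examined.

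The cost is SAP text and one extra model in the SAS software already planned, with no new data or patients. The downside is reliance on the model and on observed scores explaining later loss, though that is a weaker assumption than the one now stated. The week-24 responder comparison in item 2 is not changed by this.

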#### ***4.9 Trial progress and actual sample size description***

COG-T-CHD completed enrollment of all patients on November 17, 2023, with a total of 224 patients enrolled. We also updated the research progress information on ClinicalTrials. The actual sample size is larger than the calculated sample size, which is specifically explained here. During the initial implementation of the scheme, there were 32 subjects whose MRI data were not collected in the baseline period, which belonged to the scheme deviation. In order to ensure the integrity of the exploratory outcome indicators, 24 subjects were added to the original sample size during the inclusion process. The confidence in the original sample size was calculated using the primary outcome measure, so the primary endpoint was not missing and was not affected in any way. This study was a randomized double-blind trial, and all subjects were not blinded in the study, so the randomness of the scheme was not affected.

Reference:

